# 8. Data collection procedures & data management of study records

# 8.1 Case Report Forms (CRFs):

# Enrollment & Demographic Survey Information

Data collection instruments will be developed by the research team. Surveys and outcomes from in-depth interviews will be collected by study staff. Survey data will be collected electronically using REDCap. Compared to paper data collection, electronic data collection has the potential to be more secure, in that all data will be password protected from the moment of data collection. Data will be uploaded directly to the study's secure server from REDCap. The secure server that warehouses data will be password protected and accessible only to study personnel directly involved in data cleaning and analysis. We will plan to use wireless internet to send digital data. To protect the data, the website to which data will be uploaded will use existing well-known SSL/TLS (Secure Socket Layer/Transport Layer Security), as indicated by "HTTPS" in the URL. SSL/TLS is used by sites such as Google to protect data. All digital data will be sent and received using HTTPS.

**8.2 Record Storage:** PI and study team will maintain, and store in a secure manner, complete, accurate, and current study records throughout the study. The investigator will retain all study records for at least seven years after completion of the study. Study records include administrative documentation and regulatory documentation as well as documentation related to each participant screened and enrolled in the study, including informed consent forms, contact information forms and case report forms from all visits during the study.

# CCSG catchment Area health pilot – PROMOTE Pilot Study **8.3 Data analysis**

# For both Aim 1 & Aim 2:

**Aim 1:** Using community-based sampling in collaboration with the Fred Hutch Office of Community Engagement and Outreach, we will conduct audio-recorded, semi-structured interviews with parents of children aged 9-17 (up to *n*=12) and Bartell Drugs pharmacy staff (up to *n*=18; 9 pharmacists, 9 pharmacy technicians) to evaluate how well our proposed communication strategy match barriers and facilitators to HPV vaccination in pharmacies. Interview guides will be informed by the TDF, a widely used theoretical framework to understand behavioral determinants to successfully implement health promotion programs. Interviews will be about 90 minutes and qualitative data will be analyzed using framework-guided rapid analyses described by Gale et al. The qualitative data will be used to adapt the pharmacy staff's workflow to improve their use of the electronic forecasting system and develop a tailored vaccine communication training based on the 5A's. Adaptations made to the communication strategy will be methodically documented using Stirman's *Taxonomy of Adaptation Characteristics*.

**Aim 2:** We will evaluate the impact of the communication strategy using a pre/post implementation study design in independent pharmacies located in Western Washington state. This design is commonly used in exploratory/development studies. The communication strategy will be delivered at the pharmacy study sites by study staff members. We will use the IOF which identifies distinct implementation outcomes widely used to determine how successful implementation of an evidence-based practice, like HPV vaccination, was in a specified setting, like pharmacies. We will use validated survey measures to assess pharmacy staff's report of the *acceptability, appropriateness,* and *feasibility* of the communication strategy to support HPV vaccination. We will also conduct audits of the pharmacy electronic records to assess *adoption* of HPV vaccination, measured as the average HPV vaccination rate per pharmacist at each pharmacy. We will also assess the impact of the communication strategy on *adoption* of other adolescent vaccines using pre-post data analysis methods like Wilcoxon signed-rank test or other nonparametric tests appropriate for small sample statistics.

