Aim 2. This aim will use quantitative approaches to evaluate the feasibility and impact of the communication strategies developed in Aim 1 on adolescent vaccination rates in pharmacies, emphasizing HPV vaccination. We will use a pre/posttest quasi-experimental design to evaluate the change in vaccination rates at selected pharmacy sites after implementation of the multimodal communication strategy, as well as changes in perceptions and behavioral predictors of pharmacy staff. We will also develop an environmental scan to characterize a pharmacy's environment, vaccination workflow, and team dynamics. Conducting environmental scans of pharmacies will further contextualize barriers/facilitators to HPV vaccination.

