#### Version 3, 10/27/2022

of this aim are entirely qualitative in nature, no power calculation is required. Based on previous research studies with parents/guardians and pharmacy staff, we believe that the proposed sample sizes for Aim 1 will allow us to capture a diverse range of viewpoints and to achieve thematic saturation, where no new information is gained by additional interviewing. Sample sizes were determined based on qualitative literature that indicate that thematic saturation can be achieved with as few as 12 participants.

Aim 2: Purposive sampling of independent pharmacies in Western Washington state. As this is a pilot study aimed at understanding the feasibility, appropriateness, and potential impact of a multimodal communication strategy, a power calculation is not necessary for Aim 2. Additionally, this study is purposively designed to be of limited scope based on the Fred Hutch/UW Cancer Consortium expectations for CCSG pilot project. Our planned future study to conduct a large scale implementation trial will have resources available to hire a biostatistician who can support the study team in trial design and conducting power calculations/appropriate statistical analyses.

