# 6.5.2.B Pharmacy Staff

Recruitment & screening: [name], Director of Practice Development for the Washington State Pharmacy Association (WSPA), will introduce study information to independent pharmacy owners in Western Washington state. Pharmacy owners who are interested in participating in the study must manage/operate an independently-owned community pharmacy. Pharmacy owners will contact the study team. Pharmacy owners will provide documented confirmation of their pharmacy site's agreement of participation in the communication intervention. We will select 2 to 4 independently-owned community pharmacies with similar patient case load, demographic and community characteristics to control for internal threats to intervention validity and confounding. A waiver of written consent for the pharmacy sites will be obtained prior to the beginning of the project; thus, no written consent will be provided.

Enrollment: Once pharmacies have been enrolled into the pilot, pharmacy staff will be asked to complete a preimplementation online survey (i.e., pretest; 10-15 minutes to complete) via a survey link to assess the acceptability, appropriateness, and feasibility of providing HPV vaccination to children aged 9-17 in their pharmacies. They will be asked to attend training on the new communication strategy and employ the new communication strategy for HPV vaccinations for up to 6 months.

Once the pilot is complete, pharmacy staff will again be asked to complete a post-implementation survey (i.e., post test) in the same fashion as the pre-implementation survey.

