# CCSG catchment Area health pilot – PROMOTE Pilot Study 7.5 Vaccination audit data from the Independent Pharmacies.

The study team will establish a data use agreement with the independently pharmacies for the secure transfer and management of patient vaccination data from pharmacy sites participating in the pilot intervention. The agreement will describe variables to be included, data format, and data management. Data shall consist of the following for each patient aged 9-17 receiving vaccinations at the pilot sites: Age, sex/gender, race/ethnicity (if captured), insurance status, vaccine type, pharmacy where the patient was immunized, pharmacist who immunized the patient (using a unique code assigned to each pharmacist).

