# 7.9 Endpoints and variables

Aim 1: Qualitative information will be used to evaluate how well the proposed communication strategy matches barriers and facilitators to HPV vaccination in pharmacies for both parents/guardians and pharmacy staff. See interview question guides for the interview content.

Aim 2: Quantitative information will be collected to assess the *acceptability*, *appropriateness*, and *feasibility* of the proposed communication strategy to support HPV vaccination. See the Pre and Post Implementation Survey. Pharmacy audits will be conducted from the pharmacy electronic records to assess *adoption* of HPV vaccination, measured as the average HPV vaccination rate per pharmacist at each pharmacy. We will also assess the impact of the communication strategy on *adoption* of other adolescent vaccines (e.g., tetanus, diphtheria, acellular pertussis; meningoccocal conjugate; influenza).

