# 9. Training procedures and quality assurance

Study PI will supervise training of study staff and clinic/pharmacy staff in study procedures, including recruitment, enrollment, conduct of the interviews, and maintenance of confidentiality and privacy. Specific expertise in the conduct of qualitative research will be provided by our team's qualitative expert, who has conducted qualitative research in numerous settings. All staff have been or will be trained in the responsible conduct of human subjects' research (NIH or CITI courses).

Clinical care: No clinical care will be provided by study staff.

Adherence to protocol: For Aim 1, bi-weekly reporting of enrollment will enable us to monitor if the study is running according to approved protocols. Frequent reporting will also enable us to quickly respond to any problems that may arise during the study.

For Aim 2, we will rely on periodic reporting from the independent pharmacies who will audit their pharmacy records and report their vaccination rates. Periodic reporting will occur at baseline (Month 0) and at least 1 follow-up time point after implementation of the communication strategy (Month 2).

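### Section 8.3 names no unit of analysis and no method for HPV adoption; if the pharmacy is the unit, an exact signed-rank test on 2 to 4 sites cannot inform potential impact

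*Combined protocol and SAP*

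**What the plan says.** Section 6.1 sets up Aim 2 as an uncontrolled pre/post comparison to "evaluate the change in vaccination rates at selected pharmacy sites after implementation of the multimodal communication strategy". On the number of sites, section 6.5.2.B says: "We will select 2 to 4 independently-owned community pharmacies". Section 6.3.1 allows up to 25 staff in total and does not say how many are pharmacists.

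HPV adoption is "measured as the average HPV vaccination rate per pharmacist at each pharmacy" (section 7.9, repeated in 8.3). Section 8.3 says that audits will assess it, but gives no test, estimate or interval. The following sentence, on other adolescent vaccines, is the only one that names a method: "using pre-post data analysis methods like Wilcoxon signed-rank test or other nonparametric tests appropriate for small sample statistics". The survey scales are described as validated, again with no method. No section names a unit of analysis, an alpha or a sidedness.

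The audit extract in section 7.5 is introduced by "Data shall consist of the following for each patient aged 9-17 receiving vaccinations at the pilot sites". Its list includes the "pharmacist who immunized the patient (using a unique code assigned to each pharmacist") but no vaccination date. Section 9 adds: "Periodic reporting will occur at baseline (Month 0) and at least 1 follow-up time point after implementation of the communication strategy (Month 2"). Section 6.4 omits a power calculation because the pilot is aimed at "understanding the feasibility, appropriateness, and potential impact of a multimodal communication strategy".

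**The concern.** The main audit outcome has no stated analysis, and what the one named test can show depends on a unit that the plan leaves open. The wording of the HPV measure and of section 6.1 points to one value per pharmacy per period, hence at most four pairs. The pharmacist code in section 7.5 would also allow pharmacist pairs.

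At site level the p-value has a high floor and carries no information on effect size. At pharmacist level it treats colleagues trained in the same pharmacy as independent. If the unit is chosen after the data arrive, the same sentence of 8.3 allows either analysis. A larger trial would be planned from the size of the change and its spread between pharmacies, and 8.3 does not commit to reporting either.

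**Working it through.** The plan states no p-value, alpha or power for Aim 2, so there is no figure to reproduce.

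**Inputs from the documents.** Sites n = 2 to 4 (6.5.2.B); one HPV value per pharmacy per period (7.9, 8.3); baseline and at least one follow-up (9). Dose counts, pharmacists per site and within-site correlations are not given. The values used below are assumptions.

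**1. Pharmacy as unit: the floor.** Under the null, each of the 2^n sign patterns is equally likely. The most extreme two-sided result (all changes in one direction) has p = 2/2^n.
- n = 2: 2/4 = 0.50
- n = 3: 2/8 = 0.25
- n = 4: 2/16 = 0.125

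Enumeration of all sign patterns confirms these values. The exact sign test and any sign-flip permutation test have the same floor, so switching to another exact paired nonparametric test on site values does not help. A two-sided p below 0.05 needs at least 6 non-zero pairs (n = 5: 0.0625; n = 6: 0.031).

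**2. Pharmacy as unit: p does not reflect size.** Assume four sites, equal windows and the same change at every site. The interval is Clopper-Pearson on post/(pre + post), with each limit L converted to the odds L/(1 − L). For 10 to 18 doses, 18/28 = 0.643 has limits 0.441 and 0.814, which give 0.441/0.559 = 0.79 and, unrounded, 4.36.

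| Doses at each site | Exact signed-rank p, 4 sites | Rate ratio per site (exact 95% CI) |
|---|---|---|
| 10 to 11 | 0.125 | 1.10 (0.42–2.89) |
| 10 to 18 | 0.125 | 1.80 (0.79–4.36) |
| 10 to 30 | 0.125 | 3.00 (1.43–6.88) |

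**3. The floor belongs to the exact test.** For four equal rises each rank is 2.5. So W = 10, its null mean is 4×5/4 = 5, its variance is 4×2.5²/4 = 6.25, and z = (10 − 5)/2.5 = 2.0. The large-sample version therefore prints p = 0.046, or 0.072 with continuity correction (z = 4.5/2.5 = 1.8). The exact value is 0.125. Section 8.3 does not say which version is meant.

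**4. Pharmacist as unit.** The floor is 2/2^4 = 0.125 at 4 pairs, 2/2^6 = 0.031 at 6 and 2/2^8 = 0.008 at 8. The cost is clustering. Simulation used 100,000 runs per cell, normal changes with a shared site effect, exact critical values and an assumed 5% two-sided yardstick:

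| Sites × pharmacists | Correlation 0 | Correlation 0.20 (assumed) |
|---|---|---|
| 4 × 3 | 4.2% | 8.3% |
| 3 × 3 | 3.9% | 8.0% |

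At 0.20 the rates for 4 × 2 and 2 × 3 are 5.8% and 6.0%. The inflation thus depends on numbers that the plan does not give.

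**5. Reliability of a single-site interval.** With 10 baseline doses and a true ratio of 1.8, the nominal 95% interval covers 97.0% for Poisson counts. It covers 92.4%, 87.7% or 79.3% if the variance is 1.5, 2 or 3 times the mean (assumed).

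**The case against.** The strongest reply is that this is a deliberately small pilot. It makes no significance claim, leaves the method open, and mentions the signed-rank test only as an example for other vaccines. All of that stands, and it limits the point in four ways.

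- A reader might infer that the plan fails its own significance criterion or needs more sites. It states no alpha and no power target, so neither follows.
- A reader might infer that the signed-rank test is the planned HPV analysis. The text does not say so. If it was meant, the floor applies to HPV too; if not, HPV adoption has no method.
- A reader might infer that no signed-rank output can fall below 0.125 on four sites. That is true only of the exact version.
- A reader might infer inflated false-positive rates for the staff surveys, whose responses are linked by ID (7.4). Section 8.3 assigns no test to the survey scales, so no such error rate can be charged to the plan.

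It is also fair to say that site-level values are already implied, since the endpoint is defined for each pharmacy and section 9 has pharmacies report rates at two or more times. What is missing is a commitment to report the change per site with its uncertainty. The pilot label does not remove that need, because section 6.4 gives potential impact as one of the pilot's purposes.

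**Conclusion.** The point holds as a gap in specification with a real consequence; it should be fixed and is not a fatal flaw. Section 8.3 gives neither a unit of analysis nor a method for HPV adoption. If the pharmacy is the unit, exact paired tests on 2, 3 or 4 sites have two-sided floors of 0.50, 0.25 and 0.125 and cannot tell a 10% rise from a tripling when all sites rise. If the pharmacist is the unit, the floor drops, but the false-positive rate can roughly double when site is ignored.

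The floors are exact arithmetic and need only the site count. The doubling rests on assumed layouts of three pharmacists per site, a correlation of 0.20 and a 5% yardstick. The dose counts are illustrative.

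**What to change.** In section 8.3, name the unit of analysis for each Aim 2 outcome. Make per-pharmacy description the analysis for HPV and, in the same way, for each other vaccine, with no site-level test. For each pharmacy report:
- pre and post dose counts over equal windows, or with observation time;
- the number of pharmacists in each window;
- the planned per-pharmacist average;
- the post/pre ratio with an exact conditional 95% CI.

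If pharmacist numbers change, put them in the exposure so that the interval matches the planned endpoint: multiply the ratio and both limits by (pre pharmacists × pre time)/(post pharmacists × post time). For example, 10 to 18 doses over equal windows with pharmacists going from 2 to 3 (assumed) gives 1.80 × 2/3 = 1.20 (0.53–2.91). If a window has no doses, give the counts and the difference. Show the range of ratios across sites, show paired survey changes by pharmacy, and limit conclusions to the participating sites.

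Add a vaccination date or pre/post flag to the list in section 7.5. The data use agreement is still to be established, so this can go in now. If the rate is meant per eligible child, a denominator must be added too, because the list covers only vaccinated children.

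The cost is a paragraph of SAP text, one data field and a few lines of code. The downsides are wide single-site intervals (5 to 9 doses gives 1.80, 0.54–6.84), which are too narrow if counts vary more than Poisson.

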# 9. Training procedures and quality assurance

Study PI will supervise training of study staff and clinic/pharmacy staff in study procedures, including recruitment, enrollment, conduct of the interviews, and maintenance of confidentiality and privacy. Specific expertise in the conduct of qualitative research will be provided by our team's qualitative expert, who has conducted qualitative research in numerous settings. All staff have been or will be trained in the responsible conduct of human subjects' research (NIH or CITI courses).

Clinical care: No clinical care will be provided by study staff.

Adherence to protocol: For Aim 1, bi-weekly reporting of enrollment will enable us to monitor if the study is running according to approved protocols. Frequent reporting will also enable us to quickly respond to any problems that may arise during the study.

For Aim 2, we will rely on periodic reporting from the independent pharmacies who will audit their pharmacy records and report their vaccination rates. Periodic reporting will occur at baseline (Month 0) and at least 1 follow-up time point after implementation of the communication strategy (Month 2).

# 10. Data and Safety Monitoring Plan

All members of the research staff and the personnel employed by the community-based organization will be trained in responsible conduct of research, including enrollment of human subjects, by [name] and the research recruitment training offered by the Fred Hutchinson Cancer Center.

To protect against the risk of loss of confidentiality, only [name] and the Project Coordinator will have access to identifiable information or the study database. The study database will be password-protected and housed on a secure server at the Fred Hutch. Immediately after the semi-structured in-depth interviews data will be collected, the Project Coordinator will transport the data to locked offices at the Fred Hutch. Survey data will be

#### Version 3, 10/27/2022

collected via a secure online survey platform. Survey data will be kept in a secured cabinet under lock and key in the locked office at the Fred Hutch. For analysis, identifiable information will be removed from the datasets and participants will be assigned a unique study identifier. Audiotaped data from the semi-structured interviews will be transcribed and kept on a password-protected server. The participants will be encouraged to use a pseudonym during the semi-structured interviews, and the transcripts will identify each participant by their pseudonym.

#### 11. Ethical considerations

#### 11.1 Consent explanation

The relevant consents include the following information:

- Title
- Researchers' contact information
- Introduction
- Purpose of the study
- Procedures
- Risks, stress, or discomfort
- Alternatives to taking part in this study
- Benefits of being in the study
- Funding
- Confidentiality
- Fred Hutchinson HSD contact information
- Study participant statement
- Study participant signature page

#### **11.2 Institutional Review Board**

The study will be reviewed by the Institutional Review Board (IRB) at Fred Hutchinson Cancer Center. The study will not recruit subjects prior to approval from the Fred Hutchinson Cancer Center IRB.

#### 11.3 Risks to subjects

The primary risk of participation in the study is the loss of confidentiality. Although study staff will take all necessary precautions to protect confidential data, it is possible that participants' involvement in the research could be discovered by a third party. Employment of pharmacy staff will not be affected if staff either wish or do not wish to participate in this study.

In-Depth Interviews: Some questions may be sensitive or cause embarrassment to participants. Participants will be informed they can withdraw at any time and do not have to answer any questions if they do not want to.

Surveys/Questionnaires: Questions may cause emotional stress or embarrassment. The surveys have been designed in such a way as to minimize questions implying blame or judgment. Participants will be informed and reminded periodically that they can refuse to answer any question or stop the survey at any time.

Study staff will attend training sessions by the study investigators and receive ongoing supervision in areas related to ethical conduct, confidentiality protection, and other topics of human subject's protection. We will ensure that study staff are trained to clearly explain the purpose of the study to obtain informed consent and inform respondents about their rights and benefits without coercion to participate. We will also ensure that our interviewers inform the potential respondents about the confidentiality measures put in place to protect their privacy.

